Intervention: Thiamine 500mg IV in 100ml 0.9% saline every 12 hours for 48 hours (5 doses)

Placebo: 100ml 0.9% saline IV every 12 hours for 48 hours (5 doses)

Blood collection: Blood will be drawn at enrollment/time 0 (prior to study drug administration), 6 hours, 12 hours, 24 hours, 72, and 168 hours. Blood for all study labs will be collected by the patient's clinical nurse, using an existing intravenous or arterial line if present. Nursing or phlebotomy will perform a peripheral stick to obtain research blood only if no line is available for use. Research assistants will take all blood for immediate processing per the requirements of each lab test. Lactate and labs for SOFA score calculation will be processed in the BIDMC clinical lab. All other research assays (see list of secondary outcomes) will be completed in the BIDMC Center for Resuscitation Science Lab.

VO₂ monitoring: All patients meeting criteria for metabolic data collection (FiO₂ 60% or less and positive end expiratory pressure (PEEP) 15cm H₂O or less) will be connected to the VO₂ monitor at enrollment or as soon as the ventilator criteria are met, if still within 48 hours of enrollment. The monitor is made by General Electric, monitor version B650 with gas exchange module, and attaches in-line to the ventilator tube, between the endotracheal tube and the Y-connector. All connections and disconnections of the monitor will be done by a trained respiratory therapist, with study staff present at the bedside. The tubing is attached to sensors that collect data breath-by-breath and that data is continuously recorded while connected to a laptop with dedicated software for this purpose. At the end of the study protocol all data will be downloaded and stored in a secure CSV file.

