To investigate the association between treatment and gas metabolism data (VO₂, VCO₂ and RQ) in the first 48 hours after ROSC, we will compare the area under the curve (AUC) for each oxygen consumption variable between the treatment arms. The AUCs for the oxygen consumption variables are influenced by the number of minutes of data available, which varies between patients. To account for this, AUCs for each patient will be adjusted by dividing by the number of minutes of oxygen consumption data available for that patient. Additionally, the AUCs for the VO₂ and VCO₂ variables are influenced by the weight of the patient, and thus will also be adjusted by dividing by the bodyweight of the patient, in kilograms. The median AUCs will be compared between treatment groups using the univariate Wilcoxon rank-sum test. To

control for the known effect of temperature on oxygen consumption, we will use quantile regression to compare median AUCs between patients using the treatment assignment as the predictor and average temperature as a covariate. To examine the association between treatment and the VO₂:Lactate Ratio, we will use a linear quantile mixed model (LQMM) with the VO₂:Lactate Ratio as the outcome variable, treatment as the predictor variable and temperature as the covariate. To account for clustering of VO₂:Lactate Ratio and temperature measurements within patients, we will add a random intercept for each patient to the LQMM. We will not control for vasopressor use or sedation in the above analyses unless use of these agents is significantly imbalanced between arms.

Pyruvate dehydrogenase (PDH), S100, NSE, SOFA score, creatinine, and cellular oxygen consumption rate levels over 72 hours

To test change over time, we will compare repeated measures of each outcome listed above at each time point (0h, 24h, 72h) between arms using a linear mixed-effects model with an independent variance–covariance matrix to account for the correlation of within-patient repeated measures. Covariates in the model include treatment arm, time, and the interaction between treatment arm and time. Linear contrasts will be used to estimate the mean difference between treatment arms for each time point. To test for a difference in absolute values between arms, we will compare means or medians, as appropriate, using either a Student’s t-test or a Wilcoxon rank-sum test, respectively, at 24 and 72 hours.

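### VO₂ analyses: vasopressor and sedation adjustment is triggered by arm imbalance with no pre-dose limit, the VO₂:lactate model has no unadjusted version, and no main AUC analysis is named

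*SAP*

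**What the plan says.** All but one of the statements are in the SAP section on change in oxygen consumption (VO₂) over 48 hours, under Analysis of Secondary Outcomes.

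- **AUCs of VO₂, VCO₂ and RQ, unadjusted:** "The median AUCs will be compared between treatment groups using the univariate Wilcoxon rank-sum test".
- **The same AUCs, adjusted:** to "control for the known effect of temperature on oxygen consumption", a quantile regression is planned with "treatment assignment as the predictor and average temperature as a covariate". The averaging window is not defined.
- **VO₂:lactate ratio:** a linear quantile mixed model (LQMM) with "treatment as the predictor variable and temperature as the covariate" and a random intercept per patient. No version without temperature is planned.
- **Vasopressors and sedation:** not controlled for in any of these analyses "unless use of these agents is significantly imbalanced between arms". The period over which use is counted is not stated.

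General Principles sets a different rule for the whole SAP: no covariate adjustment unless baseline characteristics differ significantly between arms.

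**The concern.** An imbalance at baseline in a randomised trial can only be chance. An imbalance in vasopressor or sedative use after dosing may be chance, but it may also be something the treatment caused. A rule that adds these variables when the arms differ significantly acts most often when treatment has moved them, and it cannot tell the two explanations apart. The adjusted estimate is then no longer the total effect of assignment on VO₂. Part of the effect may be conditioned away. If the covariate and VO₂ share an unmeasured cause, such as severity of illness, an association may be created where there is no effect.

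Temperature raises a milder form of the same question, because its inclusion is fixed in advance and does not depend on the data. Two gaps remain. For the VO₂:lactate ratio, no comparison free of an on-study covariate will exist. For the AUCs, two analyses may disagree and the SAP does not say which one answers the question.

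VO₂ is the first of the 12 listed secondary outcomes, and it is carried into the subgroup analyses under Additional Planned Analyses.

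**Working it through.** **1. Are the covariates measured after randomisation?** The SAP does not say so outright, but its text points that way for temperature.
- The LQMM refers to clustering of "temperature measurements within patients", so temperature is a repeated measurement and not a single baseline value.
- Under VO₂ monitoring, patients are connected to the "monitor at enrollment or as soon as the ventilator criteria are met, if still within 48 hours of enrollment", so the VO₂ record starts at enrolment or later.
- The AUC analysis covers data "in the first 48 hours after ROSC". The first dose is due within 4.5 hours of ROSC, so at least 48 − 4.5 = 43.5 hours of that window follow it.
- No enrolment temperature is named as a covariate.

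For vasopressors and sedation, the text neither states nor limits the timing.

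**2. Does the VO₂ section follow General Principles?** It departs from it twice. Temperature is always included, whatever the baseline balance. The vasopressor and sedation trigger refers to use, where the general rule refers to baseline characteristics.

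**3. What can adjustment do?** The SAP gives no VO₂ effect, SD or power, so there is no figure to reproduce. The illustration below rests on assumptions. Let the true total effect be τ, let treatment shift the covariate M by a (in SDs of M), let M change VO₂ by b per SD, and let an unmeasured common cause load u on M and v on VO₂. With the variance of M within arm set to 1, a linear model adjusted for M estimates

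τ − ab − a·u·v

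while the unadjusted model estimates τ.

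- No shift (a = 0): 0.60 − 0 = 0.60. No bias.
- a = 0.3, b = 0.5, no common cause: 0.60 − 0.15 = 0.45.
- a = 0.5, b = 0.5, no common cause: 0.60 − 0.25 = 0.35.
- a = 0.3, b = −0.5 (opposing path): 0.60 + 0.15 = 0.75.
- τ = 0, b = 0, a = 0.5, u = 0.6, v = 0.6: −0.5 × 0.36 = −0.18. With v = −0.6 it is +0.18.

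**4. Simulation of the trigger rule.** There were 46 patients per arm (the planned total of 92), 600 runs, median regression, and M added only when a t-test on M gave p < 0.05. For τ = 0.60, b = 0.5 and no common cause:

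| Shift in M | Unadjusted | Always adjusted | Trigger fires | Mean under trigger rule |
|---|---|---|---|---|
| 0 | 0.60 | 0.61 | 4% | 0.60 |
| 0.3 SD | 0.61 | 0.46 | 28% | 0.54 |
| 0.5 SD | 0.57 | 0.33 | 66% | 0.37 |

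The 0.57, where 0.60 is expected, shows the simulation error, so the second decimal should not be relied on. In the null case with a common cause and a 0.5 SD shift, the always-adjusted estimates were −0.18 and +0.18. The trigger rule gave about −0.15 and +0.16.

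**The case against.** The strongest reply is that the randomised comparison is already planned where it matters most. VO₂, VCO₂ and RQ each have an unadjusted Wilcoxon test, stated before the temperature regression, and the regression has a stated purpose. The VO₂:lactate ratio, which lacks such a test, is not among the 12 listed secondary outcomes. These points stand and limit the stakes. They do not settle which AUC analysis is the main one, and they do not address the trigger rule.

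It can also be said that the unadjusted VO₂ contrast is not perfectly clean. Recording depends on meeting the FiO₂ and PEEP criteria, and the minutes of data vary by patient. Temperature may account for some of the difference in which hours were captured, and it may add precision. This stands as a reason to keep the temperature models as supportive analyses.

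The trigger could be read as an application of the baseline rule in General Principles. That is possible, but the text does not say so, and one clause would settle it.

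A reader might infer that the adjustment biases the VO₂ results toward no effect. The documents do not support a direction: they give no sign for an effect of thiamine on temperature, vasopressor use or sedation. As shown above, an opposing path or a common cause can move the estimate either way. A reader might also put a percentage on the loss from an assumed VO₂ change per degree and an assumed temperature difference between arms. The SAP gives neither quantity, so such a figure would only reflect the values chosen.

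**Conclusion.** The point holds in a limited form. As written, the vasopressor and sedation rule permits adjustment for use after dosing, triggered by a significant arm difference, and so can remove or distort part of the treatment effect in either direction. It is also out of line with the baseline-only rule in General Principles. The VO₂:lactate model has no unadjusted version, and the main analysis of the VO₂, VCO₂ and RQ AUCs is not named.

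The size is unknown. It is zero if treatment does not affect these covariates, and nothing in the SAP shows that it does. The illustrative figures rest entirely on assumed effects and shifts. That temperature is measured on study is inferred from the repeated measurements and the recording window. That vasopressor and sedation use would be counted after dosing is a possibility the wording leaves open, not something it states. The primary lactate model uses none of these covariates, so the main conclusion of the trial is not at risk.

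**What to change.** 1. Delete the rule that adds vasopressor use or sedation when they are imbalanced, or limit it to prespecified values fixed before the first dose. Report use of both by arm.
2. Name the unadjusted comparison as the main result for the VO₂, VCO₂ and RQ AUCs.
3. Add an unadjusted LQMM for the VO₂:lactate ratio and name it as the main result for that ratio.
4. Keep the temperature-adjusted quantile regression and LQMM as labelled supportive analyses, and define the window over which temperature is averaged.

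The cost is SAP text only; no extra data are needed. The downside is that the main VO₂ result may be somewhat less precise than a temperature-adjusted one, which is a further reason to keep the adjusted models alongside it.

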Prior to unblinding or analysis, oxygen consumption data will be cleaned using an algorithm designed by our research team in R version 4.1.1 (R Foundation for Statistical Computing, Vienna, Austria). This automated algorithm excludes VO₂ data (and the corresponding value for carbon dioxide production, or VCO₂) if one or more of the following criteria is met: all values recorded in the 10 min following a change in FiO₂ of 10%, all values recorded while FiO₂ is >61% (61% used in order to capture all situations when the ventilator is set for an FiO₂ of 60% or less, as the monitor reports this number to two decimal places and a set number of 60% may be recorded as 60.54%), all values deviating 15% or more from the mean of the previous five values and the next five values (i.e, deviating 15% from the mean of the ten neighboring data points), and all VO₂ values out of physiologic range unless these are persistent for more than 30 minutes, as these measurements are considered artifacts. Values that will be considered out of physiologic range are VO₂<80 mL/kg/min or VO₂>800 mL/kg/min. We allow these values if they persist for at least 30 min and if they are not excluded per the algorithm for other reasons, as critically ill post-arrest patients can sometimes have values well outside of standard normal range, due to temperature, medication use such as sedatives and neuromuscular blockade and/or alterations in metabolic function. The respiratory quotient (RQ) is calculated as the ratio of VCO₂/VO₂ at each time point. After data is run through the algorithm and still prior to unblinding, there is a final visual review of a graphical print-out of all data points for each patient to provide a secondary confirmation that values were kept or dropped appropriately.

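### The VO₂:lactate ratio model has no weight indexing and no time term, so it carries body-size noise and can pool a pre-dose value; its scheduled pairs end at 24 h

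*SAP*

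**What the plan says.** All of the VO₂ analysis stands in the SAP under *Analysis of Secondary Outcomes*, *Change in oxygen consumption (VO₂) over 48 hours*.

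- **AUCs.** The plan notes that "the AUCs for the VO₂ and VCO₂ variables are influenced by the weight of the patient" and so these "will also be adjusted by dividing by the bodyweight of the patient, in kilograms".
- **Ratio.** In the same paragraph, "we will use a linear quantile mixed model (LQMM) with the VO₂:Lactate Ratio as the outcome variable, treatment as the predictor variable and temperature as" its only covariate. For clustering, "we will add a random intercept for each patient to the LQMM". No weight division, weight term, time term, list of time points or rule for pairing VO₂ with a lactate draw is given.
- **Window.** The 48 h wording belongs to the AUC sentence: "in the first 48 hours after ROSC, we will compare the area under the curve (AUC"). The ratio sentence names no period.
- **Unit.** The cleaning rule earlier in the section reads: "Values that will be considered out of physiologic range are VO₂<80 mL/kg/min or VO₂>800 mL/kg/min".
- **Lactate draws.** Under *Protocol*, *Blood collection*, blood is taken at enrollment before study drug and then at "6 hours, 12 hours, 24 hours, 72, and 168 hours".
- **VO₂ monitoring.** The patient is connected at enrollment or when ventilator criteria are met, provided this is within 48 h of enrollment.

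**The concern.** The plan accepts that body size drives VO₂ and removes it from the AUCs, then leaves it in the ratio. Lactate does not grow with body size, so nothing in the denominator offsets it. The random intercept allows for repeated values from one patient. It does not take body size out of the treatment contrast, because treatment also varies only between patients.

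The model also has one treatment coefficient and no time term, whereas the primary lactate model has time and a treatment-by-time interaction. Any pair formed at 0 h, before the first dose, is therefore averaged into the treatment effect. Finally, lactate is scheduled over only part of the VO₂ monitoring period, and the plan does not say which part the ratio describes. At stake are precision, some dilution of effect, and analyst choices left open in a supporting analysis.

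**Working it through.** The plan gives no figure for the ratio, so there is none to reproduce.

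**1. Body size does not cancel.** If VO₂ is proportional to weight, two patients with equal VO₂ per kg and equal lactate but weights of 60 and 100 kg (illustrative) have ratios that differ by 100/60 = 1.67-fold.

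**2. Size of the noise.** Lactate means and SDs come from *Sample Size Calculations*. Assumptions not in the documents: weight CV 15–30%, VO₂-per-kg CV 15–25%, VO₂ proportional to weight, log-normal and independent components.

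Log variance = ln(1 + CV²).

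| Component | CV | Log variance |
|---|---|---|
| Lactate 6 h | 2.2/3.8 = 0.58 | 0.289 |
| Lactate 12 h | 2.2/3.5 = 0.63 | 0.333 |
| Lactate 24 h | 2/2.9 = 0.69 | 0.389 |
| VO₂ per kg | 0.15 / 0.25 | 0.022 / 0.061 |
| Weight | 0.15 / 0.30 | 0.022 / 0.086 |

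Inflation = (lactate + VO₂ per kg + weight) / (lactate + VO₂ per kg).

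- Smallest (24 h, weight CV 15%, VO₂-per-kg CV 25%): (0.389 + 0.061 + 0.022) / (0.389 + 0.061) = 1.05; standard error × 1.02.
- Largest (6 h, weight CV 30%, VO₂-per-kg CV 15%): (0.289 + 0.022 + 0.086) / (0.289 + 0.022) = 1.28; standard error × 1.13.
- Ranges by draw: 1.06–1.28 at 6 h, 1.06–1.24 at 12 h, 1.05–1.21 at 24 h.

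These figures are for one draw. Lactate spread is the largest component in every case.

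**3. Dilution by the 0 h pair.** Suppose the effect is 0 at 0 h, constant afterwards, and pairs are weighted equally. Then the pooled estimate is about 3/4 of the post-dose effect with pairs at 0, 6, 12 and 24 h, 2/3 with 0 h and two later pairs, and 1/2 with 0 h and one later pair. Where VO₂ was not yet recorded at 0 h there is no such pair and no dilution. For a quantile model this is an approximation.

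**4. Coverage.** Counted from enrollment, the scheduled lactates in 0–48 h are at 0, 6, 12 and 24 h, so 48 − 24 = 24 h have none. Counted from ROSC, with enrollment 0 to 4.5 h later, the 24 h draw falls at 24 to 28.5 h, which leaves 19.5 to 24 h. The 72 h draw lies beyond the 48 h VO₂ outcome. A patient first connected after 24 h has no scheduled pair.

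**5. Unit.** If VO₂ is already per kg, as the cleaning rule prints it, dividing its AUC by kilograms indexes it twice. If it is not, the printed unit is wrong and the ratio is unindexed. The two statements cannot both hold.

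**The case against.** The strongest answer is the printed unit. If VO₂ is recorded in mL/kg/min, the ratio is already indexed and the weight point disappears. That does not rescue the plan, because the AUCs would then be divided by weight twice, and the stated reason for dividing them makes sense only for VO₂ that is not yet per kg. What stands is that the plan is contradictory here and the conflict must be part of the point.

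A reader might infer that the ratio was planned for 48 h and fails to cover it. The text does not support this: the 48 h belongs to the AUC sentence and the section heading. What is firm is that no window, time points or pairing rule are fixed.

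A reader might also turn the variance inflation into an equivalent loss of patients. That goes too far, since it rests on assumed CVs and on a log scale that the planned model, as described for the ratio, does not use.

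Nor is this bias. Under randomization, weight adds noise and chance imbalance, and *General Principles* allows adjustment when baseline characteristics differ significantly. That rule is triggered by significance and would not bring weight in by default, so it helps only partly. It is also true that the plan does not say a 0 h pair enters the model, and late connection to the monitor will remove some. The dilution is therefore conditional.

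**Conclusion.** The point holds as a cheap improvement to a supporting analysis; the ratio is not among the listed *Secondary Outcomes*. Followed as written, the model leaves body size in the treatment contrast. Under the assumptions above, this costs roughly 5–28% in log-ratio variance at a draw (standard error 2–13% larger), which is modest beside the spread of lactate itself. Any 0 h pair shrinks the treatment estimate toward no effect. Results from scheduled draws can speak only to 0–24 h and should be described that way. The conflict between the unit in the cleaning rule and the division by kilograms stands without any assumption.

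**What to change.** Amend the ratio text in the SAP before the data are analysed:

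1. Form the ratio from weight-indexed VO₂.
2. Use the scheduled 6, 12 and 24 h lactates as the post-dose outcomes. Pair each with the mean of the retained VO₂ values in a fixed window around the draw, for example 30 minutes either side.
3. Keep the 0 h ratio out of the post-treatment outcome, or use it as a baseline covariate.
4. State that the ratio covers 24 h.
5. Reconcile the mL/kg/min unit in the cleaning rule with the division of the AUCs by kilograms.

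The cost is wording only: VO₂ and lactate are already collected, and weight is already needed for the AUCs. There is a small downside. Patients with no VO₂ recording around the 6, 12 or 24 h draws contribute nothing, and stated coverage is 24 h. If 0 h is used as a covariate, patients without a 0 h pair need a stated rule.

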Cerebral Performance Category (CPC) and Cerebral Performance Category-Extended (CPC-E) score assessments: CPC and CPC-E will be assessed just prior to hospital discharge, at 30 and 90 days. Research staff will approach patients for assessment of CPC-E prior to hospital discharge. The CPC-E includes several questions testing logical thinking, attention and memory. The outpatient portion, which will be assessed in addition to the inpatient portion after hospital discharge/at 30 and 90 days, also includes questions about functional status and return to work. The CPC score will also be assessed by research staff prior to discharge. Phone calls to the patient will be made at 30 and 90 days (if the patient is no longer in the hospital).

Outcome Measures

Primary Outcome: Lactate change

The primary outcome is change in lactate over 24 hours following enrollment.

Secondary Outcomes:

1. Absolute level and change in VO₂ over 48 hours
2. Absolute level of lactate over 72 hours
3. Absolute level and the change in pyruvate dehydrogenase (PDH) quantity, activity and specific activity over 72 hours
4. Absolute level and the change in S100 levels over 72 hours
5. Absolute level and the change in neuron-specific enolase (NSE) levels over 72 hours
6. Mortality (hospital discharge, 30 and 90 days)
7. Cerebral Performance Category (CPC) score (hospital discharge, 30 and 90 days)
8. Cerebral Performance Category-Extended (CPC-E) (hospital discharge, 30 and 90 days)
9. Absolute level and the change in Sequential Organ Failure Assessment (SOFA) Score SOFA over 72 hours
10. Acute renal failure during first 7 days following arrest
11. Absolute level and change in cellular oxygen consumption rate over 72 hours
12. Absolute level and the change in creatinine over 72 hours

Sample Size Calculations:

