The statistical analyses and reporting will adhere to the CONSORT guidelines. All tests will be two-sided, a p-value <0.05 will be considered significant, and all confidence intervals will have 95% coverage. All analyses will be conducted on a modified intention-to-treat basis only including participants receiving at least the first dose of the study medication. In a double-blind trial, this approach is unbiased while increasing precision. Analyses will not be adjusted for covariates unless there are significant differences in baseline characteristics between study arms.

Baseline Characteristics

A description of the baseline characteristics will be presented by treatment arm. Categorical variables will be summarized by frequencies and percentages. Percentages will be calculated according to the number of patients for whom data are available. Continuous variables will be summarized using mean+/-standard deviation or median (interquartile range) based on the distribution of the data.

Analysis of Primary Outcome

We will compare repeated measures of lactate levels at each time point (0h, 6h, 12h, 24h) between arms using a linear mixed-effects model with an independent variance-covariance matrix to account for the correlation of within-patient repeated measures. Covariates in the model include treatment arm, time (as a categorical variable with four levels, defined as baseline, 6 hours, 12 hours, and 24 hours), and the interaction between treatment arm and time. Linear contrasts will be used to estimate the mean difference between treatment arms for each time point. If a patient dies before 24 hours, levels will be imputed by carrying forward the last known value before the event with a 20% penalty. A sensitivity analysis will be performed in which patients who die before 24 hours are assigned the last known value before the event without a penalty.

Analysis of Secondary Outcomes

Lactate levels over 72 hours

To test for a difference in absolute lactate level values, we will compare means or medians, as appropriate, between arms using either a Student's t-test or a Wilcoxon rank-sum test, respectively, at 6, 12, 24 and 72 hours.

Change in oxygen consumption (VO₂) over 48 hours

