Mortality, Cerebral Performance Category (CPC) Score, and Cerebral Performance Category-Extended (CPC-E) Score at hospital discharge, 30 days, and 90 days

Proportions of patients who do not survive to hospital discharge, 30 days, and 90 days will be compared between treatment arms using Fisher’s exact test. Fisher’s exact test will also be used to compare the proportion of patients who have a favorable CPC score at the same time points, with favorable CPC score defined as a score of 1-2 and unfavorable a CPC of 3-5. CPC-E will be analyzed between treatment arms as a continuous variable in survivors to the time point of interest using either a Student’s t-test or a Wilcoxon rank-sum test, based on the distribution of the data.

Acute renal failure in the first 7 days after study drug initiation

Acute renal failure in the first 7 days after study drug initiation will be determined using the Kidney Disease Improving Global Outcomes (KDIGO) criteria for Stage 3 acute kidney injury/kidney failure. These criteria are as follows:

1. An increase in creatinine to $\geq 3 \times$ baseline (baseline defined as enrollment [post-arrest pre-study drug] creatinine value) OR
2. An increase in creatinine by $\geq 0.3\text{mg/dL}$ from baseline to $\geq 4\text{mg/dL}$ OR
3. Initiation of renal replacement therapy

Patients who die before 7 days and who do not meet the above criteria before death or transition to comfort measures only status will be classified as not having acute renal failure. Proportions of patients who have renal failure will be compared between groups using Fisher's exact test. Patients who already have end-stage renal disease (defined as being on dialysis/renal replacement therapy prior to arrest) will be excluded from the acute renal failure analysis.

Additional Planned Analyses

Pre-planned subanalyses of the primary outcome and of the secondary outcomes of mortality and VO_2 will be performed stratified by arrest duration, dichotomized into <15 minutes and ≥ 15 minutes and in the group of patients with baseline thiamine deficiency (plasma vitamin B1 level ≤ 7 nmol/L). Based on feedback from the DSMB, we will also perform subanalyses based on 0 hour lactate, stratified by ≤ 5 and >5 .

Analysis of Adverse Events

Rates of serious expected and unexpected adverse events will be reported by arm assignment. Proportions of patients with adverse events will be compared between the treatment arms using Fisher's exact test.

Statistical Software

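### The SAP has no rule for creatinine drawn after new renal replacement therapy starts, so the mean comparison shifts in favour of the arm with more of it

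*SAP*

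**What the plan says.** Item 12 of the SAP's Secondary Outcomes is "Absolute level and the change in creatinine over 72 hours". Under Analysis of Secondary Outcomes, creatinine shares one paragraph with PDH, S100, NSE, SOFA and cellular oxygen consumption rate:

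- **Change:** "To test change over time, we will compare repeated measures of each outcome listed above at each time point (0h, 24h, 72h) between arms", by a linear mixed model. "Covariates in the model include treatment arm, time, and the interaction between treatment arm and time".
- **Level:** a t-test or a Wilcoxon rank-sum test at 24 and 72 hours. "To test for a difference in absolute values between arms, we will compare means or medians, as appropriate".

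RRT appears in one place only, the 7-day acute renal failure outcome. There, "Initiation of renal replacement therapy" is enough by itself to meet the stage 3 definition, whatever the creatinine. Patients on dialysis before the arrest "will be excluded from the acute renal failure analysis". That exclusion does not extend to the creatinine analysis, and it does not concern RRT that starts after enrolment.

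**The concern.** RRT removes creatinine from the blood, so a value drawn afterwards no longer tracks kidney function. The SAP's two renal outcomes then treat the same patient differently. The acute renal failure outcome records a failure, while the creatinine analysis takes the lowered number as an ordinary measurement. No scheduled analysis point lies between 24 and 72 hours, so a creatinine that peaks before RRT starts in that interval may never enter the analysis.

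At stake is the direction of bias in one secondary outcome. The patients with the worst renal course have their worsening understated, and the arm with more of them gains most.

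**Working it through.** **1. Is there a rule anywhere in the SAP?** The creatinine paragraph has no censoring, worst-value or worst-rank rule, no RRT term and no sensitivity analysis. General Principles does not supply one: "Analyses will not be adjusted for covariates unless there are significant differences in baseline characteristics between study arms". RRT begun after enrolment is not a baseline characteristic. Elsewhere the SAP does set rules for disturbed values. For lactate it says: "If a patient dies before 24 hours, levels will be imputed by carrying forward the last known value before the event with a 20% penalty". It also discards VO₂ values after FiO₂ changes. Creatinine has nothing comparable. That values are used as measured is inferred from this silence; the SAP does not say so in words.

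**2. Inputs.** From the SAP: 92 patients randomised 1:1, so 46 per arm (a size set on lactate). The SAP gives no creatinine mean, SD or RRT rate, so there is no stated figure to reproduce. Every creatinine value and RRT count below is an assumption.

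**3. Shift in the difference of means.** If RRT lowers creatinine by L mg/dL on average in both arms, the shift in favour of the arm with more RRT is L × (difference in RRT proportions).

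One excess patient with L = 3: 3/46 = 0.065 mg/dL. Two: 6/46 = 0.13 mg/dL.

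| Lowering L (mg/dL) | 5-point excess | 10-point excess | 20-point excess |
|---|---|---|---|
| 1 | 0.05 | 0.10 | 0.20 |
| 2 | 0.10 | 0.20 | 0.40 |
| 3 | 0.15 | 0.30 | 0.60 |

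With equal counts and equal lowering, the shift is zero.

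**4. Worked example for the 72-hour level.** Assume 7 vs 2 patients on new RRT, creatinine 5.0 before RRT and 2.0 on it, and 1.5 in everyone else.

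- Pre-RRT values: (39×1.5 + 7×5.0)/46 = 93.5/46 = 2.03; (44×1.5 + 2×5.0)/46 = 76/46 = 1.65. Difference 0.38.
- As measured: (39×1.5 + 7×2.0)/46 = 72.5/46 = 1.58; (44×1.5 + 2×2.0)/46 = 70/46 = 1.52. Difference 0.05.
- Lost: 5×3/46 = 0.33, about 86% of the difference in means. The arm with more RRT still looks worse.

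**5. Second set of assumptions.** Take 1.5 in patients without RRT; in RRT patients, 4.5 if not dialysed and 2.0 as measured.

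- RRT in 15% vs 5%: 0.10 × (4.5 − 1.5) = 0.30 becomes 0.10 × (2.0 − 1.5) = 0.05. Simulation with 46 per arm gave 0.297 and 0.046.
- RRT in 25% vs 5%: 0.60 becomes 0.10. Simulation gave 0.590 and 0.092.

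**6. When the sign can reverse.** On the level scale, the mean dialysed value must fall below the mean of patients without RRT. On the change scale, dialysed patients must fall more than the others do. For example, let RRT patients start at 2.5 and reach 4.5 undialysed or 1.8 as measured, while the others change by −0.1. A 10-point RRT excess then gives 0.10 × (2.0 + 0.1) = +0.21 undialysed, but 0.10 × (−0.7 + 0.1) = −0.06 as measured.

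**7. Rank test.** In the step 4 example the RRT patients hold the top ranks at 2.0 just as at 5.0. Either way U = 7×44 + 0.5×7×2 + 0.5×39×44 = 308 + 7 + 858 = 1173, so the test is unchanged. With real spread among the other patients some ranks would be lost, but less than the shift in means suggests.

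**The case against.** The strongest reply is that the effect may be small and the renal signal is not lost. RRT must start before the 24- or 72-hour draw to matter. One or two excess patients move the mean by only 0.07 to 0.13 mg/dL even with a 3 mg/dL lowering. The acute renal failure outcome still counts every new RRT start within 7 days, and an as-measured analysis is a definable treatment-policy choice. All of this limits the harm, but it does not repair the creatinine comparison. The SAP also does not present as-measured analysis as a deliberate choice.

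A reader might infer three stronger things that the SAP does not support:

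- **That a dialysed patient is recorded as improving, or that the arm with more RRT will look better.** The example in step 4 shows attenuation without reversal. If its RRT patients stood at 4.0 at 24 hours, before RRT, the 24-hour means would be 86.5/46 = 1.88 vs 74/46 = 1.61, again worse in that arm. Those patients would add an extra 24-to-72-hour fall of (7 − 2)×2/46 = 0.22 mg/dL, but the SAP names no such contrast. Its contrasts are between arms at each time point.
- **That 86% of the evidence disappears.** That figure applies to means under one set of assumed values, not to the rank test.
- **That SOFA is distorted in the same way.** The SAP does not state how the renal part of SOFA is scored, so this cannot be judged from it.

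**Conclusion.** The point holds as an unaddressed bias in one secondary outcome. Followed as written, the creatinine analyses take RRT-lowered values as kidney function, although the same SAP treats starting RRT as renal failure. The dependable consequence is understated worsening and a mean comparison shifted in favour of the arm with more new RRT.

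The range of 0.05 to 0.60 mg/dL rests on an assumed lowering of 1 to 3 mg/dL, equal between arms, and an RRT excess of 5 to 20 points before the draw. The per-patient figure of 0.065 mg/dL also assumes values from 46 patients per arm; with fewer measured, each excess patient weighs more. The primary outcome is untouched. The change is worth making because it is cheap and because a rule chosen after arm-level RRT counts are known would be open to criticism.

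**What to change.** Add a rule to the creatinine analyses for patients who start RRT after enrolment, applied at every time point after RRT begins:

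- **Wilcoxon test:** assign the worst rank.
- **Mixed model and t-test:** use the highest creatinine recorded before RRT began. State whether values drawn outside the 0, 24 and 72 hour schedule count.
- **Sensitivity analysis:** repeat with values as measured.
- **Reporting:** show the number of patients on new RRT by arm beside the creatinine results.

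The cost is a sentence or two in the SAP and a few lines of code. RRT initiation is already needed for the acute renal failure outcome; its timing relative to the blood draws must be available too. The downside is a carried value in a few patients. It may be too low where RRT was started for a reason other than high creatinine, and if unscheduled values count, peaks are drawn from them for RRT patients only. The sensitivity analysis shows how much the result depends on the rule. No change to SOFA scoring is asked for.
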